Protocol Outline

Protocol Title: Use of Text messaging for positive reinforcement to help improve quality of life in pediatric patients with obesity.

Protocol Version: 3

Protocol Date: 6/13/2019

Principal Investigator: [name]

Research Team: [name], [name], [name]

I. Abstract

Background and Significance:

Pediatric obesity has become a public health crisis in the United States. Although research has been conducted surrounding this topic, rarely does this research utilize mobile technology to promote accountability in children. Limited research has been done looking at any potential relationship between use of mobile apps and the benefit for quality of life in this patient population.

Hypothesis:

We hypothesize that providing positive reinforcement through text messaging to children living with obesity will improve their overall quality of life.

Specific Aims:

This study primarily aims to evaluate the utility of mobile technology in improving the quality of life of children living with obesity. Another aim of this study is to assess mobile technology's role in promoting accountability in children with obesity.

Brief Methods:

We will recruit patients between the ages of 13 and 18.

We will administer a pre and post survey regarding quality of life for pediatric obese patients. This survey has been well studied and used in numerous other studies. The family will be given recommendations on various ways to increase physical activity weekly. These patients will then receive positive reinforcement for completed exercises through text messages.

II. Background and Significance/Preliminary Studies

Pediatric obesity has become a public health crisis in the United States. The prevalence of overweight and obese children has increased anywhere from two to three-fold among various age groups in the last few decades. The American Academy of Pediatrics (AAP) has outlined the unique role of pediatricians in the prevention of pediatric obesity. By following children throughout a large portion of their lives, pediatricians can encourage healthful behaviors and promote family engagement¹. The AAP has also emphasized the importance of health supervision

to promote increased levels of physical activity and early recognition of pediatric obesity in patients².

In public health practice, HRQOL can be utilized to understand a patient's perception of their own physical and mental health³. In addition, the assessment of quality of life in children can pose unique problems due to children's perception of illness, interpretation of questions, and perspective on disease time course⁴. One study has found that children in the United States living with a chronic medical condition are among those with the poorest HRQOL⁵. Several studies have shown that patients with obesity have lower self-reported health, especially in the youngest adolescents (ages 12-14).

Many studies have been conducted to determine the utility of mobile applications or text messaging systems in changing the behavior of children with pediatric obesity. Few, however, have used mobile applications or text messaging to assess accountability in health decisions and the quality of life outcome for these children.

One particular study, concluded that the use of coaching through twice-weekly text messages and telephone contact every other month improved the quality of life outcome in children ages 2-12 years old with a BMI > 85th percentile from primary care practices in Massachusetts⁶. Many studies have created applications or web-based interventions of their own to decrease pediatric obesity. FitKids, a community-level intervention in Memphis, TN, utilized a mobile website to support parents and children in achieving healthier lifestyles¹⁰. Another study used a multi-component intervention, "HAPPY ME," that included a wearable device¹¹.

It is evident that the majority of studies conducted include the interplay of multiple resources and forms of technology to promote behavior change. Studies have also been conducted to determine the quality and content of commercially available mobile applications. In 2014, a large iTunes app search coded 62 total apps for adherence to the American Academy of Pediatrics guidelines for preventing pediatric obesity and found scores to be consistently low¹². Another study showed similar results, indicating that commercially available apps for children had moderate quality overall and scored highest in functionality rather than information quality¹³.

These findings suggest that many commercially available mobile applications are insufficient in changing behavior outcomes in children with pediatric obesity. On the other hand, little has been discovered about the impact mobile applications can have on the quality of life in these children by holding them accountable for their health decisions.

This research project hopes to add to the literature other ways to help improve quality of life for this patient population with simple text messaging and potentially help them improve their overall lifestyle and general health.

III. Study Aims

Our study hopes to investigate the relationship between positive reinforcement for exercise activities in pediatric patients living with obesity and quality of life. We hypothesize that providing positive reinforcement through text messaging to children living with obesity will improve their overall quality of life.

IV. Administrative Organization

Patients will be recruited from the Loyola University Medical Center outpatient clinic during their well visit with their primary care physician. The principal investigator or co-PI will screen the patients being seen in the outpatient center by age and BMI that are automatically populated for each visit on the schedule page. Once a patient is identified as a potential research subject, the PI or co-PI will approach the attending to let them know that the patient is a good candidate and confirm that they are an appropriate patient for the study. If the attending agrees, then the research team will approach the family are about the study while they are in clinic to see if they are interested in participating in the study.

V. Study Design

This will be a prospective interventional cohort study following a group of patient patients with obesity. Informed consent will be obtained from the parents from a member of the research committee. Informed assent will also be obtained from the patient from a member of the research committee.

VI. Study Procedures

We will review the schedule in the pediatrics department daily and approach all patients that meet our inclusion criteria listed below. Per standard of care for patients with obesity, they have a scheduled follow up for a weight check at regular intervals that can include one month, 3 months or 6 months.

Inclusion criteria:

- A. Ages 13-18
- B. BMI >95%
- C. Has a cell phone

Exclusion criteria:

- A. Developmental delay and inability to read
- B. Does not have a cell phone

The 40 subjects will be randomly assigned to either a control group or an intervention group.

Survey

A 23 item PedsQL 4.0 pre-survey will be administered to pediatric patients to establish a baseline at their wellness visits. The parent of the patient will also complete the PedsQL survey. The patients' BMI and blood pressure will be recorded. At the end of the 6 month period, the same PedsQL 4.0 will be administered again to both the patient and parent at the scheduled 6 month weight check that is standard of care.

We will use a text message application created by the Loyola informatics team. This application will be able to text the subjects using their cell phone number via an email service from the provider. For example, [name]. This allows the research team to send text messages through an application without using a personal phone number. In addition, it offers automatic responses that will save them when sending messages to the patient.

For six months, patients in the study will receive a text message twice per week.

Text messaging

There will be two groups within this study—a control group and an intervention group. For the control group, they will receive two text messages weekly. The first text message will ask if they completed the recommended activity. When they respond, they will receive a second text message stating, "Thanks for your response."

In the intervention group, the first text message will ask if they completed the recommended activity. If they respond yes, they will receive a positive reinforcement response comprising the words "Great job! We're so proud of you! Keep up the good work!". If they respond no, they will receive a text message stating "Thanks for your response".

Study Activities: See attached schedule for details

The weekly activities we will recommend for the subjects include:

1. Walking for 30 minutes 3 times a week
2. Speed walk for 30 minutes 3 times a week
3. Walk up and down stairs for 30 minutes 3 times a week
4. Jogging for 30 minutes 3 times a week
5. Jumping jacks for 30 minute 3 times a week

Data:

All patient data will be stored in a secure REDCap database located at hsddb.luhs.org/redcap.

Statistical analysis:

In this study, patients who are age 18 and under with a BMI in at least the 95th percentile will be randomized to an intervention or control text-messaging cohort using a 1:1 random allocation. Subsequently, they will be asked to complete assigned exercises. For six months, these patients will receive a text message twice per week asking whether they completed their assigned exercises. For those in the intervention group, when they respond "Yes", they will receive a positive reinforcement response comprising the words "Great job! We're so proud of you! Keep up the good work!". Otherwise, when they respond "No", they will receive a message saying "Thanks for your response". For those assigned to the control group, they will always receive the message "Thanks for your response" regardless of whether they complete or do not complete the assigned exercises.

Six months following randomization, one goal of the proposed study is to test the null hypothesis that average total score on PEDSQ4.0 questionnaire between the two groups are equal. With a proposed sample size of 20 assigned to receive the positive reinforcement response and 20 assigned to receive the control response (N = 40), the study will have power of 80.0% to yield a statistically significant result. This computation assumes a mean difference between the two

cohorts of 14.8 points (corresponding to means of 81.8 for the positive reinforcement cohort and 67.0 for the control response cohort) and a common within-group standard deviation of 16.3 points⁷. This computation also assumes the criterion for significance (alpha) is 0.05 and that the test will be 2-tailed, meaning an effect in either direction will be interpreted.

Recommended Protocol Text for the Analysis Plan

Patients under age 18 with a BMI in at least the 95th percentile will be asked to complete assigned exercises and will receive text messages asking them if they completed such exercises. At baseline and the end of the study, the participants will complete the 23-item PEDSQ4.0 assessment. For each participant, the baseline value will be subtracted from the 6-month value. An independent samples t-test will be used to compare this delta score between the cohort assigned to receive the positive reinforcement response and the cohort assigned to receive the control response. For this comparison, the normal distribution assumption of the delta score will be assessed using QQ plots and outliers will be assessed using box plots. The homogeneity of variances assumption will be assessed using Levene's test. If any parametric assumption is strongly violated, a non-parametric Wilcoxon rank-sum test may be used to compare ranked PEDSQ4.0 scores between the two cohorts. All analyses will be completed using SAS version 9.4 (Cary, NC) by a Biostatistician in the Clinical Research Office.

VII. Safety Monitoring Plan

There are no adverse events that could be associated with text messages we will send to the subjects. We will send these text messages on Monday early evening between the 5pm to 6pm. We chose this time because they will not be in school and are unlikely to be driving or doing activities that they could be distracted from when they receive the text, which could cause harm.

If there is an adverse effect, we will ask the subjects to notify the principal investigator of the project. We will review safety information once a month.

VIII. Literature Cited

References

- 1 Daniels et al. The role of the pediatrician in primary prevention of obesity. *Pediatrics*. 2015;136(1):e275
- 2 Snyder, et al. American academy of pediatrics. *Congenital Heart Disease*. 2012;7(2):200-201.
- 3 Health-Related Quality of Life (HRQOL) | CDC. (2018). Retrieved from <https://www.cdc.gov/hrqol/index.htm>
- 4 Eiser, et al. A review of measures of quality of life for children with chronic illness. *Archives of disease in childhood*. 2001;84(3):205-211.
- 5 Simon, et al. Assessment of children's health-related quality of life in the united states with a multidimensional index. *Pediatrics*. 2008;121(1):e118.
- 6 Swallen, et al. Overweight, obesity, and health-related quality of life among adolescents: The national longitudinal study of adolescent health. *Pediatrics*. 2005;115(2):340.

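### Does the unclear number of weekly text questions (one or two) undermine the comparison of the two arms?

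*Combined protocol and SAP*

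**What the plan says.** Five places in the combined protocol and SAP bear on the number or timing of the texts.

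- Section VI, Statistical analysis, attaches the frequency to the question itself: "these patients will receive a text message twice per week asking whether they completed their assigned exercises". Replies are then described separately, by arm.
- Section VI, Survey, has a general sentence for everyone: "For six months, patients in the study will receive a text message twice per week". It does not say what the text contains.
- Section VI, Text messaging, says of the control group that "they will receive two text messages weekly. The first text message will ask if they completed the recommended activity", and then "When they respond, they will receive a second text message stating" thanks for the response. The intervention paragraph that follows also speaks of a first text that asks the question, but gives no weekly count.
- The Recommended Protocol Text for the Analysis Plan says only that participants "will receive text messages asking them if they completed such exercises".
- Section VII, Safety Monitoring Plan, gives one sending time: "We will send these text messages on Monday early evening between the 5pm to 6pm". The reason follows: "We chose this time because they will not be in school and are unlikely to be driving".

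Section VI also refers to an attachment: "Study Activities: See attached schedule for details". It is not in the text available for review. It introduces the list of exercises and may not cover messaging.

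**The concern.** The praise reply is the only planned difference between the arms, and it is sent only when a participant answers a question with yes. The number of questions therefore caps how much of the intervention anyone can receive.

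Read at face value, the control paragraph names a weekly total of two and then appears to use up both messages, one as the question and one as the reply. That leaves one question per week, against two in the Statistical analysis text. A single named sending day seems to support the lower count.

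If the conflict were real and unresolved, a reader could not reproduce the intervention or check the messaging application against the protocol. If it meant that the arms were prompted differently, the comparison would mix praise with frequency of contact. The reasoning on timing would also cover only the Monday slot, with no day or time stated for a second question.

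**Working it through.** **1. The plan's own figure.** Inputs from section VI, Statistical analysis: 20 per arm, means 81.8 and 67.0, SD 16.3, two-sided alpha 0.05.

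- Difference: 81.8 − 67.0 = 14.8.
- Standardised difference: 14.8 / 16.3 = 0.908.
- Noncentrality: 0.908 × √(20/2) = 2.87, on 38 degrees of freedom.
- Power from the noncentral t distribution: 79.9%. The plan states 80.0%, so the figure is reproduced.

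No term in this calculation is a message count. The planned analysis, an independent-samples t-test on the six-month change in PedsQL score, has none either.

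**2. Size of the ambiguity.** Six months is taken as 24 to 26 weeks (assumption), with 20 intervention participants and one automatic reply per answered question.

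| | One question per week | Two questions per week |
|---|---|---|
| Questions per participant | 24 × 1 = 24 to 26 × 1 = 26 | 24 × 2 = 48 to 26 × 2 = 52 |
| Messages received per week | 1 (unanswered) or 2 (answered) | 2 (none answered), 3 (one) or 4 (both) |
| Ceiling on praise replies, whole arm | 20 × 24 = 480 to 20 × 26 = 520 | 20 × 48 = 960 to 20 × 52 = 1,040 |

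The ratio is 2 throughout the first and third rows. The praise figures are ceilings, reached only if every question is answered yes; they do not estimate the praise delivered.

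**3. Does the control paragraph fix a second value?** If replies count towards its weekly total of two, one question gives that total only in weeks when it is answered, and two questions give it only in weeks when neither is. Neither schedule yields two messages every week, so the paragraph cannot be an exact count of all messages. If replies do not count, the total refers to questions, and first and second give the order within each exchange. The intervention paragraph uses the word first with no weekly count, which shows that the authors do use it for order. The general sentence under Survey closely parallels the Statistical analysis sentence and covers both arms.

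So one sentence states the question frequency outright, another is most consistent with it, and one paragraph is loosely worded and can be read differently.

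**4. Are the arms treated alike?** The general sentence and the Statistical analysis sentence each cover all patients. The Safety Monitoring Plan's slot is not split by arm. The weekly count in the control paragraph is missing from the intervention paragraph, but nothing there gives a different one. On either schedule, the planned contrast is praise against a neutral reply after a yes.

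**The case for a change.** The strongest case for acting is that the lower count is a natural reading of the control paragraph, that the higher reading would send up to four messages a week to someone who answers both questions, and that no second sending day appears anywhere. The praise reply is the whole intervention, and clearing up the wording is cheap: one consistent statement and a check of the application's settings.

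Much of this stands. The description is unclear, a frequency of twice per week beside a single named day is a real gap, and the reason given for the timing has been written for that slot only. A report of the trial would need to state the schedule actually used.

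Two parts do not carry through. First, the text does not set two definite values against each other: it has one explicit statement and one paragraph that can be read either way. The Monday sentence names a slot without excluding others. Second, nothing at stake reaches the inference. It may be said that twice the praise could produce a larger effect, so that power depends on frequency after all. But the assumed 14.8-point difference is given as a pair of means and an SD, not built up from a number of praise replies, and the documents offer no relation between the two. Settling the count would give no basis for a different sample size.

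**Conclusion.** The concern is right that the wording is inconsistent, but it does not call for a change to the design or the analysis. It is a clerical matter in the description of the intervention. The Survey, Text messaging, Statistical analysis and Safety Monitoring Plan texts must be reconciled on questions per week and on sending day and time, together with the attached schedule if it covers messaging. Which schedule is meant is for the investigators to say; the documents do not settle it beyond doubt.

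The ambiguity amounts to at most a factor of 2 in the ceiling on praise, 24 to 26 against 48 to 52 questions per participant. The effect on the stated power is nil, and so is the effect on the form of the t-test.

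This rests on three assumptions: six months is 24 to 26 weeks, each answered question draws one reply, and both arms follow the same schedule. The text supports the last of these and nowhere contradicts it. Were the arms in fact prompted at different rates, the conclusion would not hold.

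### The 80.0% power figure is for the six-month PedsQL score, but the planned test is on change from baseline, whose SD is given nowhere

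*Combined protocol and SAP*

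**What the plan says.** The sample-size paragraph (section VI, Statistical analysis) sets the goal, six months after randomisation, to "test the null hypothesis that average total score on PEDSQ4.0 questionnaire between the two groups are equal". It assumes a difference of 14.8 points, "corresponding to means of 81.8 for the positive reinforcement cohort and 67.0 for the control response cohort", with "a common within-group standard deviation of 16.3 points", two-sided alpha 0.05 and 1:1 allocation of 40 patients. From these it concludes that "the study will have power of 80.0% to yield a statistically significant result". It names no test and makes no allowance for loss to follow-up.

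The analysis is described under Recommended Protocol Text for the Analysis Plan. There, for each participant, "the baseline value will be subtracted from the 6-month value". Then: "An independent samples t-test will be used to compare this delta score". The distributional check is on the same variable: "the normal distribution assumption of the delta score will be assessed using QQ plots".

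**The concern.** The two paragraphs concern different variables. The first powers a comparison of score levels at six months; the second tests change from baseline. Under randomisation the expected group difference is the same for both, so 14.8 carries over. The SD does not: the SD of change depends on the baseline SD and on the correlation (rho) between baseline and six-month scores, and the document gives neither.

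The power statement is the only justification offered for N = 40. If it does not apply to the planned test, the sample size has no stated support.

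**Working it through.** **Inputs from the document.** Difference 81.8 − 67.0 = 14.8; SD 16.3; 20 per arm; two-sided alpha 0.05.

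**Inputs I assume.** Rho, a baseline SD equal to the six-month SD, and the loss rates. The document gives none of these, so ranges are shown.

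**1. The plan's own figure.** For a two-sample t-test, the noncentrality is difference / (SD × √(2/n)) with 2n − 2 degrees of freedom. For the six-month score it is 14.8 / (16.3 × √0.1) = 2.871 on 38 df, and power is 79.9%. The stated 80.0% is therefore reproduced, as a t-test of the six-month score with all 40 analysed. Since the paragraph names no test, both the test and the full analysis set are inferred from this match.

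**2. What the planned test needs.** Solving the same formula for the SD, a change-score t-test with 20 per arm reaches 80% only if the SD of change is at most 16.28.

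**3. The range for the planned test.** With SD 16.3 at both visits, the SD of change is 16.3 × √(2(1 − rho)).

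| Assumed rho | SD of change | Noncentrality | Power, 20 per arm | n per arm for 80% |
|---|---|---|---|---|
| 0 | 23.05 | 2.030 | 50.8% | 40 |
| 0.3 | 19.29 | 2.427 | 65.7% | 28 |
| 0.5 | 16.30 | 2.871 | 79.9% | 21 |
| 0.7 | 12.63 | 3.707 | 95.1% | 13 |

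At rho = 0.5 the SD of change equals 16.3, so the stated figure returns, just under 80%; that is why the last column shows 21.

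**4. Loss to follow-up.** On the variable that was powered, 18 evaluable per arm gives 75.4% and 16 gives 70.0%.

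**5. ANCOVA of the six-month score, adjusted for baseline.** The residual SD is 16.3 × √(1 − rho²), with 2n − 3 df. The variance of the difference is multiplied by 1 + F/(2n − 2), where F follows F(1, 2n − 2), to allow for chance baseline imbalance; power is averaged over F. No baseline SD is needed.

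| Evaluable per arm | rho 0 | rho 0.3 | rho 0.5 | rho 0.7 | rho at which power is 80% |
|---|---|---|---|---|---|
| 20 | 78.8% | 82.4% | 89.0% | 97.1% | 0.17 |
| 18 | 74.0% | 77.9% | 85.2% | 95.4% | 0.37 |
| 16 | 68.5% | 72.5% | 80.4% | 92.7% | 0.49 |

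A simulation with 400,000 draws per cell agreed to within 0.1 percentage point. For 80% power, ANCOVA needs 19, 16 and 12 per arm at rho 0.3, 0.5 and 0.7, against 28, 21 and 13 for the change-score t-test.

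**The case against.** A change-score t-test is valid in a randomised trial, and no shortfall has been shown. If rho is 0.5 or more with equal SDs, the planned test has essentially the stated power or better. The smallest repair is one stated SD of change with the power at that value; ANCOVA is an efficiency gain and is not needed to cure the mismatch. All of that stands. It is why the figure is called unsupported and not overstated, and why the smaller repair is kept below as an alternative.

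A sharper objection is that ANCOVA does not secure 80% with 40 patients unless some correlation is credited. At rho = 0 it needs 21 evaluable per arm, and with an assumed 20% loss that means 21/0.8 = 26.25, so 27 randomised per arm. This is correct. The proposal keeps N = 40 and states the power honestly; it does not promise 80%. A sponsor who wants 80% without crediting any correlation would need more patients.

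One could also read 16.3 as the SD of change. The text does not support that: the value stands beside score-level means, under a null hypothesis about the score, and is never called an SD of change.

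**Conclusion.** The concern holds. The 80.0% is arithmetically right for the six-month score and unsupported for the change score that will be tested. The direction of the error is unknown: with equal SDs assumed at both visits, power of the planned test runs from 66% at rho 0.3 to 95% at rho 0.7. The absence of a loss allowance is a separate weakness.

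The 79% for ANCOVA is a minimum over rho only. It remains conditional on a true difference of 14.8, a six-month SD of 16.3 and all 40 patients analysed. The trial stays analysable, so this should be fixed but is not fatal.

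**What to change.** **Analysis text.** Replace the delta-score and t-test sentences with: *The six-month PedsQL total score will be compared between cohorts by ANCOVA adjusted for the baseline score, analysed as randomised.* Check the assumptions on the model residuals instead of the delta score, and bring the rank-based fallback into line with the same outcome and adjustment.

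**Sample-size text.** Replace the 80.0% with: *about 79% for this ANCOVA with 20 evaluable per cohort, a true difference of 14.8 and SD 16.3, taking no credit for baseline-to-six-month correlation (82%, 89% and 97% at assumed correlations of 0.3, 0.5 and 0.7); with 16 evaluable per cohort, an assumed 20% loss, about 68% (73%, 80% and 93%).* If one figure is preferred, give the zero-correlation value at the sponsor's expected evaluable number, with the loss rate labelled as an assumption.

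**Alternative.** If the change-score t-test is kept, state one justified SD of change and the expected evaluable number, and give the power at those values.

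**Cost.** Two rewritten paragraphs, with no new data and no extra patients provided the restated power is accepted. ANCOVA uses one degree of freedom and assumes a common baseline slope in both arms. The stated power falls slightly with no loss, and further once loss is allowed for.

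### The between-group test on change in PedsQL is valid but fixes the baseline slope at 1; using the baseline score as a covariate would probably be more precise at almost no cost

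*Combined protocol and SAP*

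**What the plan says.** Section VI, Survey, provides for baseline measurement: "A 23 item PedsQL 4.0 pre-survey will be administered to pediatric patients to establish a baseline". The same instrument is given again at six months.

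The text headed Recommended Protocol Text for the Analysis Plan then defines the outcome: "For each participant, the baseline value will be subtracted from the 6-month value". The test follows: "An independent samples t-test will be used to compare this delta score between the cohort assigned to receive the positive reinforcement response" and the control cohort. Diagnostics are attached to that variable: "the normal distribution assumption of the delta score will be assessed using QQ plots and outliers will be assessed using box plots", with Levene's test for equal variances. If an assumption clearly fails, "a non-parametric Wilcoxon rank-sum test may be used to compare ranked PEDSQ4.0 scores between the two cohorts". No regression, ANCOVA or other covariate model is specified anywhere.

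The power statement, under Statistical analysis in Section VI, concerns the score itself six months after randomisation. The aim there is to "test the null hypothesis that average total score on PEDSQ4.0 questionnaire between the two groups are equal", with 20 per arm, a 14.8-point difference and "a common within-group standard deviation of 16.3 points". It gives no SD of change, no baseline SD and no correlation between the two visits.

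**The concern.** Subtracting baseline does use the baseline score, but with its coefficient fixed at 1. The coefficient that minimises variance is rho × (six-month SD / baseline SD). When that is well below 1, subtraction over-corrects and adds baseline noise to the outcome. ANCOVA estimates the coefficient from the same data.

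Two things are at stake in a 40-patient trial with no power margin.

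- **Precision.** The stated 80% power belongs to a variable with SD 16.3. The planned test uses a different variable whose SD is not given.
- **Chance imbalance.** If the arms differ by D at baseline, the change-score contrast is shifted by (1 − slope) × D. When the slope is below 1, the shift favours the arm that started lower. ANCOVA removes it.

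**Working it through.** **Inputs from the documents:** 20 per arm, difference 14.8, six-month SD 16.3, "the criterion for significance (alpha) is 0.05", two-sided.

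**Assumptions not in the documents:** rho; the baseline SD, written as 16.3/k with k = six-month SD / baseline SD; and all 40 participants analysed.

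**1. The plan's own figure.** SE = 16.3 × √(2/20) = 5.15. Noncentrality = 14.8/5.15 = 2.87. The noncentral t with 38 df gives 79.9%, which matches the stated 80.0%.

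**2. Variances per patient.**
- Change score: 16.3² × (1 + 1/k² − 2·rho/k), 38 df.
- ANCOVA: 16.3² × (1 − rho²) × 37/36, 37 df. The factor 37/36 is the expected cost of estimating the slope at N = 40.

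Example with k = 1 and rho 0.3:
- Change score: 265.69 × 1.4 = 371.97, so SD 19.29.
- ANCOVA: 265.69 × 0.91 × 37/36 = 248.49, so effective SD 15.76.
- Expected 95% CI half-width: 2.024 × √(371.97 × 2/20) = 12.3 points, against 2.026 × √(248.49 × 2/20) = 10.1 points.

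**3. Power at 14.8 points.**

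| rho | Change, k = 0.8 | Change, k = 1 | Change, k = 1.25 | ANCOVA, any k |
|---|---|---|---|---|
| 0.3 | 54.7% | 65.7% | 73.8% | 82.4% |
| 0.5 | 68.5% | 79.9% | 86.3% | 89.0% |
| 0.7 | 87.4% | 95.1% | 97.3% | 97.1% |

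The SD of change equals 16.3 when rho = 1/(2k), that is 0.625, 0.5 and 0.4 for k = 0.8, 1 and 1.25. Below those values the change score has less than the planned power. ANCOVA reaches 80% from rho of about 0.2 (80.4%).

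**4. Where the change score is at least as good.** With k = 1 the condition is 2(1 − rho) ≤ (1 − rho²) × 37/36, so rho ≥ 72/37 − 1 = 0.946. At k = 1.25 it holds for rho from 0.68 to 0.88, and at k = 0.8 it never holds. The worst case for ANCOVA is a slope of exactly 1. The variance ratio change/ANCOVA is then 36/37 = 0.973, a loss of 2.7%.

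**5. Conditional shift.** With equal SDs, one SE of the baseline difference is 5.15 points. The shift is (1 − rho) × 5.15 = 3.6, 2.6 and 1.5 points at rho 0.3, 0.5 and 0.7.

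**6. Validity.** In simulation (bivariate normal, 100,000 trials per cell, the k and rho values above), type I error was 4.8–5.1% for both methods and mean error at most 0.03 points.

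**7. The fallback.** The ranked scores could be deltas or six-month scores. One baseline-adjusted rank analysis ranks both scores across arms, regresses six-month ranks on baseline ranks, and compares the residuals by t-test. With k = 1, rho 0.3 and 14.8 points it has about 80% power in simulation, against about 64% for Wilcoxon on change and about 77% for Wilcoxon on six-month scores. The order reverses against Wilcoxon on change when the slope is near 1. At k = 1, rho 0.9 and an assumed 7 points it is 76% vs 82%. At k = 1.25, rho 0.8 and an assumed 9 points it is 74% vs 79%.

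**The case against.** The planned analysis is a standard, valid test that already uses baseline. The size of any gain rests on two quantities that the documents do not give. Over the grid above it runs from about 28 power points (k = 0.8, rho 0.3: 82.4 − 54.7) to none (k = 1.25, rho 0.7). With equal SDs and rho 0.7 it is 2 points. All of this stands, and it limits the point to an efficiency recommendation.

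Three stronger readings are tempting, and the documents do not support them.

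- **The t-test on change is biased or wrong.** It is not. Allocation is randomised, the error rate is held, and the shift in step 5 is conditional on a chance imbalance and averages to zero.
- **The planned test falls short of 80% power.** This cannot be shown. Without rho and the baseline SD, power could be below or well above 80%. That the power statement describes six-month scores while the test uses change is a separate planning mismatch, and it does not make this point more serious.
- **Baseline adjustment costs at most 2.7% in every form, so the Wilcoxon fallback should also be replaced.** The 2.7% bound applies only to the parametric ANCOVA. An adjusted rank method can lose about 5 to 6 power points, and how it compares with the plan depends on which scores the plan means to rank.

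**Conclusion.** The point holds as a cheap improvement that should be made, not as an error. The planned contrast fixes at 1 a slope that the trial can estimate. Unless the true slope is close to 1 (0.946 or more with equal SDs), ANCOVA is more precise. With equal SDs the gain is about 17, 9 and 2 power points at rho 0.3, 0.5 and 0.7. It is larger if the baseline SD exceeds the six-month SD, and smaller or absent if it is the lower of the two.

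These figures assume a six-month SD of 16.3, a true difference of 14.8 points, 40 analysed participants (the plan states no allowance for dropout) and approximate normality. Confidence in the size is medium, because rho and the SD ratio are unknown. The direction of the trade does not depend on them: the possible gain is large and the parametric loss is capped at 2.7% of variance efficiency.

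The optional fallback needs clarifying, not replacing.

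**What to change.** Before outcome data are examined, change the analysis plan text as follows.

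- **Primary analysis:** *The six-month PedsQL 4.0 total score will be compared between arms by linear regression (ANCOVA) on treatment arm with the baseline total score as covariate; the adjusted mean difference and 95% CI will be reported.* Add that these are reported whether or not the fallback is triggered, since a rank test gives no estimate in PedsQL points.
- **Diagnostics:** apply the QQ plots, box plots and Levene's test to the model residuals.
- **Supportive analysis:** keep the t-test on change from baseline.
- **Fallback:** its trigger and optional status can stay. State whether it ranks deltas or six-month scores. A baseline-adjusted rank analysis is an option, with the trade-off shown in step 7.

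The cost is rewording the test and diagnostic sentences, a clarifying phrase in the fallback, and one degree of freedom (38 to 37). No new data are needed. If the slope is near 1, the ANCOVA gives up at most 2.7% of variance efficiency.
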